Daily at 8:00 pm, participants will complete self-reports of alcohol craving, including Visual Analog Scale for alcohol and tobacco craving (VAS); Penn Alcohol Craving Questionnaire (PACS) (Flannery et al., 1999), Beck Depression Inventory-II (BDI-II), Beck Anxiety Inventory (BAI), Obsessive Compulsive Drinking Scale (OCDS), and Alcohol Urge Questionnaire (AUQ). Nursing staff will complete clinician-administered instruments for alcohol withdrawal assessment (see below). Participants will have PRN access to over the counter medications to treat headache, gastrointestinal upset and body aches.

Each day of the CRU stay, the CRU nurse will administer the Systematic Assessment for Treatment of Emergent Events (SAFTEE) (Johnson et al., 2005). This standardized, structured

instrument is specifically adapted for use in substance use disorder clinical trials, to collect information on incidence and severity of medication side effects and adverse events.

To determine if the degree of elevation of CORT in response to GR blockade by MIFE correlates with any of our outcome measures, each morning upon wakening and at bedtime on the CRU, a salivary cortisol sample is obtained. Baseline samples will be collected on day 1, prior to beginning study medications. Measurement of CORT in saliva is not invasive and multiple samples per day are easily obtained. Unlike serum CORT, salivary CORT is unbound to protein and reflects the physiologically relevant fraction. For each sample, subjects chew a pad for 90 sec, which they then place into a capped salivette. Saliva is harvested by centrifugation and stored in a cryotube at -70 until assayed in duplicate (Diagnostic Systems Laboratories; Webster, Texas). The intra- and inter-assay coefficients of variation are below 5%. As we expect variability in CORT within and across MIFE doses, these data will be included in our analyses.

Because MIFE is occasionally associated with hypokalemia, serum potassium level is obtained before study procedures on day 1 and again on day 7 and at the 1 week follow-up visit. Potassium replacement will be addressed as needed.

Outpatient procedures for HC: Healthy control subjects will complete the study as a 4-day outpatient protocol.

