AUD subjects will complete medically supervised alcohol detoxification as in our earlier studies (McCaul, [name], Eissenberg et al., 2000; McCaul et al., 2001; Bencherif et al., 2004; Weerts et al., 2008; Weerts et al., 2011; [name] et al., 2013; Weerts et al., 2013). Participants will be required to wear a mask before nurse, staff or housekeeping enter the room. All AUD subjects will receive intravenous D5W NS over the first 12 hours following admission. The Clinical Institute Withdrawal Assessment - Alcohol Revised (CIWA-Ar) (Sullivan et al., 1989), which includes 10-items (nausea/vomiting, tremor, paroxysmal sweats, anxiety, agitation, tactile disturbances, auditory disturbances and visual disturbances), will be completed by CRU nurses every 4 hours while the participant is awake. This well-validated clinical tool will assess alcohol withdrawal symptom severity, and is the gold standard to guide benzodiazepine (BZ) administration during symptom-driven withdrawal management (Saitz et al., 1994). We have successfully studied alcohol withdrawal in our prior research. Scores on the CIWA-Ar are sufficiently elevated that we are able to see reductions in withdrawal severity as a result of research pharmacological intervention. If the CIWA score is ≥ 12 the subject is given intravenous diazepam (5mg) or lorazepam (1mg). The CIWA score is repeated 1 hour after the first diazepam dose. If the score remains ≥ 10 then a second intravenous diazepam dose (5mg) or lorazepam dose (1mg) is given. This procedure is repeated one more time and if the CIWA-Ar score remains ≥ 10 then the participant is transferred to the Bayview ED and terminated from the protocol. Based on our previous study, we anticipate that few subjects will require BZ treatment since we exclude subjects who report a history of withdrawal complications. If systolic blood pressure increases above 180 and/or diastolic blood pressure increases above 105, we may administer atenolol 25 mg po and then titrate as needed. Subjects will be removed from the protocol for seizures, hallucinations, or disorientation or following three doses of diazepam or lorazepam. At that point in time, the physician on call will be contacted. The subject will be transported to the Johns Hopkins Bayview Emergency Department for care. The subject is now terminated from the study.

MIFE Administration:

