MIFE has a rapid onset of action and achieves peak plasma levels within 1 - 2 hrs of oral dosing. Peak plasma levels and bioavailability increase as a function of dose but are not directly proportional to dose. However, plasma concentrations of MIFE metabolites do increase in direct proportion to dose; metabolites have antiglucocorticoid activity and contribute to long-acting drug effects (Pomara et al., 2002). MIFE is effective with once-a-day dosing. The half-life is 40 hrs following a single dose and 84.6 hrs following multiple doses. Following discontinuation of MIFE, plasma levels are detectable for up to 2 weeks (Heikinheimo et al., 2003). For this study, we selected to use the high MIFE dose of 1200mg, based on recent clinical trials for other neuropsychiatric disorders associated with HPA-axis dysfunction, and that 1200 mg MIFE has been safely administered over extended periods (MIFE Investigator Brochure, Corcept Therapeutics). This study only exposes subjects to MIFE for up to 6 days. We are not planning to reduce MIFE dose during such a brief treatment period. If a subject experiences significant medication side-effects or any serious adverse event or if the participant declines to continue medication, then we will discontinue that participant from the study. It

should be noted that inpatient subjects are under continuous nursing observation throughout the CRU stay and thus adverse events can be identified and addressed rapidly. HC subjects will be instructed to call the study doctor if they have any adverse events. Subjects will be randomized to active MIFE and placebo on a 2:1 ratio.

In the proposed study, MIFE will be administered under an IND ([name] 124365). MIFE (300 mg) and matching placebo will be provided by Corcept Therapeutics, Menlo Park, CA. We will overencapsulate the medication and placebo as necessary. The Johns Hopkins Bayview Investigational Drug Services (IDS) will maintain the inventory and dispense the medication. MIFE absorption and elimination are not affected by age, body weight, BMI, race or sex (Mifepristone Investigator Brochure, Corcept Therapeutics).

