Each subject will participate in an initial assessment, and a possible second assessment visit for completion of medical history, vital signs and laboratory tests. AUD participants will be admitted to the CRU for 6 nights. HC participants, who participate in the study on an outpatient basis, will continue MIFE dosing and salivary sample collection at home. For AUD participants, there are two follow-up visits at 1 and 2 weeks following CRU discharge. For HC participants, there is one follow-up visit at 1 week following the second fMRI. It is anticipated that subjects will complete all study procedures within a 6 month period.

c. Blinding, including justification for blinding or not blinding the trial, if applicable.

Staff and subjects will be blind to the alcohol and MIFE doses administered during this study to reduce expectancy effects.

d. Justification of why participants will not receive routine care or will have current therapy stopped.

Subjects are not seeking treatment for their AUD; they will not currently be engaged in therapy.

e. Justification for inclusion of a placebo or non-treatment group.

A placebo MIFE dose is included for comparison with the active drug effects and to control for expectancy effects.

f. Definition of treatment failure or participant removal criteria.

A participant will be removed from the study if s/he experiences a moderate or severe adverse event, is noncompliant with study or CRU rules, or if it is determined by the study physician to be unsafe to continue.

g. Description of what happens to participants receiving therapy when study ends or if a participant's participation in the study ends prematurely.

MIFE dosing is discontinued at the time of discharge from the study.

5. Inclusion/Exclusion Criteria

Healthy, non-treatment seeking, 21-60 years old, male and female subjects will be recruited through the media. Recruitment uses a mix of newspaper, radio, and on-line advertisements. Based on the 2011 census, the Baltimore metropolitan area is mostly Caucasian (61%) or African-American (30%); the remaining 9% is Asian (4%) and persons reporting two or more races (5%); 8.8% of the population report Hispanic ethnicity.

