Aim 3. AMR variables include: total number of alcohol drinks earned; total number of responses during the 60-minute session; distribution of responses for alcohol versus money; progressive ratio breakpoint for alcohol (maximum completed ratio value); response rate (responses/min) and response latency to compete the ratio for alcohol and money. We also measure alcohol craving using the Tiffany Craving Scale; these data will be summarized using peak score and area under the curve. The normality of the outcome measures will be examined first and two sample t-test, or equivalent non-parametric methods will be used to compare the outcomes between GR antagonist-treated group and placebo-treated group.

Aim 4: Subjective and physiological data will be collected repeatedly during the alcohol sensitivity session. We will test outcome measures between the two groups using mixed-effect linear regression with random intercept. Baseline measures will be examined as potential confounding factors and added to the model if needed. We will summarize the baseline adjusted area under the curve and peak values of the outcome measures and compare between the two groups using repeated measure ANCOVA model.

Aim 5: We use the SAFTEE to collect comprehensive side-effect information. We will construct negative binomial generalized linear regression model with the number of events as the dependent variable and grouping and other covariates as independent variables. The model will give the difference in the logs of expected numbers of side effect events between the two treatment groups. We will then also make comparisons taking into consideration the duration and severity of the side effects, which are both collected in SAFTEE for each reported side effect event. A summary side-effect score will be calculated as the sum of the duration multiplying the severity of each side effect event.

Secondary analyses: Another objective of this study is to generate power estimation for a full-size future clinical trial.

d. Early stopping rules.

Individual subjects will be discontinued from the protocol if they experience a moderate-to-severe adverse reaction to MIFE. They also will be discontinued for repeated rule violations on the CRU. The study will be discontinued if there is a pattern of MIFE-related AEs or SAEs.

8. Risks

a. Medical risks, listing all procedures, their major and minor risks and expected frequency.

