- Subjects with potassium levels below the normal range at screening will be excluded. We will also monitor potassium on days 1 and 7 (AUD participants only), and at the 1 week follow-up. Potassium will be administered if clinically needed.
- Based on data from studies and clinical trials, which encompass over 1500 subjects and patients treated for one to two weeks with MIFE doses ranging from 300 mg/day to 1800 mg/day, the risk for development of adrenal insufficiency in persons without Cushing Syndrome is low. Specifically, in studies of psychotic depression and in volunteers with antipsychotic drug induced weight gain as well as healthy volunteers and subjects with hepatic and renal impairment who participated in PK, PD, and DDI studies, there were no AEs of adrenal insufficiency reported (Personal Communication, Corcept Therapeutics). Still, in the current study, subjects will be monitored for the development of the signs and symptoms of adrenal insufficiency (weakness, nausea, increased fatigue, hypotension) during the CRU stay and during outpatient visits. Once on the CRU and following MIFE administration, we monitor for hypoadrenalinism by measuring blood pressure and heart rate along with all vital signs q6 hours. For inpatient participants, we also will be asking questions q6 hours regarding emergence of symptoms of hypoadrenalinism, including the development of fatigue, nausea, vomiting, abdominal pain, loss of appetite, light headedness, arthralgias, and myalgias. Outpatient participants will be asked these questions once daily either in person or by phone. If an AUD subject on the CRU is thought to be developing hypoadrenalinism, we will discontinue the MIFE, support blood pressure with intravenous fluids and infuse 8mg of dexamethasone intravenously. Outpatient healthy control participants will be provided with oral dexamethasone 8 mg to take home. They will be given an instruction sheet (see supplemental study documents) that advises them of the symptoms of adrenal insufficiency and advises them to call [name] if these symptoms start to develop. This dose is more than adequate to reverse the glucocorticoid receptor blockade. The proposed single dose of dexamethasone is routinely used in the determining the etiology of Cushing Syndrome. In patients with impaired glucose tolerance or frank diabetes mellitus, this dose of dexamethasone can transiently increase blood sugar; however, in our study, participants with impaired glucose tolerance are excluded. Dexamethasone will only be used in the unlikely event of adrenal crisis in which we do not anticipate any negative side-effects from the treatment.

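### Section 4f removes a participant for any moderate or severe adverse event; 7d and the dosing text set different rules, and 4f does not exempt withdrawal or blood pressure rises that the plan treats on study

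*Combined protocol and SAP*

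**What the plan says.** Four places in the combined protocol and SAP decide who leaves the study early.

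- Section 4f (participant removal criteria): "A participant will be removed from the study if s/he experiences a moderate or severe adverse event". Failure to comply with the rules of the study or the CRU, and a study physician's finding that continuing is unsafe, are further grounds. Cause is not mentioned.
- Section 7d (early stopping rules): "Individual subjects will be discontinued from the protocol if they experience a moderate-to-severe adverse reaction to MIFE". Repeated rule violations on the CRU are a second ground.
- Section 4a, MIFE Administration: the condition for discontinuation reads "If a subject experiences significant medication side-effects or any serious adverse event or if the participant declines to continue medication". The word 'significant' is not defined.
- Section 4a, Alcohol Withdrawal Management: a CIWA-Ar score of 12 or more is treated with a benzodiazepine, and a further dose follows if the score is still 10 or more after an hour. Systolic pressure above 180 or diastolic above 105 may be treated with atenolol. The termination rule is "Subjects will be removed from the protocol for seizures, hallucinations, or disorientation or following three doses of diazepam or lorazepam", with transfer to the emergency department if the score stays at 10 or more after the repeat doses.

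On the CRU, nurses give the SAFTEE every day "to collect information on incidence and severity of medication side effects and adverse events". The CIWA-Ar is described as an instrument "which includes 10-items (nausea/vomiting, tremor, paroxysmal sweats, anxiety, agitation" and other signs. Section 8b monitors for hypoadrenalism by asking about symptoms, "including the development of fatigue, nausea, vomiting, abdominal pain, loss of appetite, light headedness, arthralgias, and myalgias".

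**The concern.** Staff on the unit need to know whether a given event ends a subject's participation, and the answer depends on which section they open. The rule in 4f is the broadest as to cause. It also stands beside a withdrawal procedure that is plainly meant to keep and treat subjects who have become unwell.

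The timing makes this matter. Dosing starts on day 1, after randomisation. The second scan is on day 4, the stress test and alcohol motivated responding session on day 5, and the alcohol sensitivity session on day 6. These supply most of the primary outcomes in section 7a. An AUD subject removed on day 2 or 3 contributes to none of them, and an HC subject removed then has no second scan. Daily SAFTEE collection would also end, although adverse events are the first primary outcome listed. Subjects who discontinue medication are asked only for post-discharge follow-up.

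Withdrawal is an expected part of the AUD stay, not a rare accident, so the case that 4f leaves open is foreseeable.

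**Working it through.** The plan gives no figure on this point, and no arithmetic applies. The check is to put typical events to each rule in turn.

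| Event | 4f | 4a, MIFE Administration | 7d | 4a, Alcohol Withdrawal Management |
|---|---|---|---|---|
| Moderate, not serious, not caused by MIFE | Remove | No | No | Not addressed |
| Moderate, not serious, reaction to MIFE | Remove | Only if called significant | Remove | Not addressed |
| Serious, not caused by MIFE | Remove if graded moderate or severe | Remove | No | Only if it is one of the listed events |
| CIWA-Ar 12 or more, settles after one or two benzodiazepine doses | Remove if recorded as a moderate adverse event | No, unless serious | No, if not due to MIFE | Treat and keep |
| Blood pressure above 180 or 105 | Remove if recorded as a moderate adverse event | Only if serious or a significant drug side-effect | Only if a moderate-to-severe reaction to MIFE | May treat; no removal stated |

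1. Row one is a definite difference. A moderate, non-serious event unrelated to drug leads to removal under 4f alone.
2. The rules do not contradict each other in the strict sense. All can be obeyed together by applying 4f whenever it is met. But that makes the condition in 7d that the event be a reaction to MIFE redundant, and it could override the treat-and-keep procedure for withdrawal.
3. Rows four and five depend on labelling. No section says that withdrawal or a treated blood pressure rise is graded as an adverse event, and none says that it is not. No section defines moderate or severe either.
4. The labelling question is a practical one. Nausea and vomiting appear both as a CIWA-Ar item and in the hypoadrenalism symptom list in 8b. One symptom could therefore be kept (read as withdrawal), stopped (read as a MIFE reaction) or removed (read as a moderate event of any cause).
5. The physician clause in 4f does not settle the matter. It is an additional ground for removal and gives no discretion to keep a subject who has had a moderate event.
6. On direction, Hypothesis 2a expects MIFE to reduce withdrawal, so removals for withdrawal would tend to fall on placebo. Removals for drug-caused events would fall on MIFE. These pull in different directions, and the documents give no rate of moderate events in either arm.

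**The case against.** The strongest reply is that the clash with the withdrawal procedure is conditional and that the documents lean against it. Sections 7a and 7b list adverse events as a primary outcome and CIWA-Ar severity separately as a secondary one. The daily procedures likewise separate the SAFTEE from the withdrawal instruments. A reader could reasonably let the detailed withdrawal algorithm govern over one summary sentence in 4f. The plan also expects little treated withdrawal: "we anticipate that few subjects will require BZ treatment since we exclude subjects who report a history of withdrawal complications". All of this stands, and it is why the withdrawal part is put as a missing exemption and not as a contradiction. It does not touch the first row of the comparison, where 4f and 7d differ whatever is decided about withdrawal.

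A second reply is that removal for any moderate event is a defensible, conservative rule in a Phase I study giving 1200 mg of MIFE with alcohol, and that it is easy to apply blind. That is fair as a design choice. But the plan has not made that choice consistently, because 7d already asks for attribution to MIFE.

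A reader might go further and infer that 4f will bias the results by a known amount or in a known direction. The documents do not support this. Section 8b reports that over 98% of past subjects were withdrawn without protocol termination, and section 5 reports that over 90% completed. It is tempting to turn these into a loss of under 2% (fewer than 0.02 × 75 = 1.5 AUD subjects) or at most 10%. The first figure counts withdrawal-related terminations, which this plan's own withdrawal criteria would produce with or without a change to 4f. The second arose under earlier studies' rules and cannot cap losses under a stricter one. Neither measures the extra removals caused by the wording of 4f.

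**Conclusion.** The point holds as an inconsistency in a stated rule. It is certain that 4f has no causality condition, that 7d has one, that the dosing text uses a third and partly undefined threshold, and that 4f exempts nothing handled by the withdrawal procedure. It is also certain that removal before day 4 loses primary measurements.

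It is not established that staff would grade treated withdrawal as a moderate adverse event, or that removals would be many or would favour one arm. Size and net direction cannot be computed, so none is claimed. The case for the change is that staff need one rule and that the correction is cheap, not that a large bias is expected. It should be fixed.

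**What to change.** 1. Use one rule in 4f, 7d and the MIFE Administration text. Remove a participant for: a moderate-to-severe adverse event judged, blind to arm, at least possibly related to study drug; any serious adverse event; a study physician's judgement that it is unsafe to go on; failure to comply with the rules of the study or the CRU; or declining medication. The last two must be kept so that harmonising the wording does not delete existing criteria.
2. State in 4f that withdrawal symptoms and blood pressure rises managed under Alcohol Withdrawal Management are not removal events unless they meet that section's own termination criteria.

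The cost is a wording amendment, a blinded relatedness judgement by the study physician, and a slightly narrower automatic removal rule. Physician discretion to remove is retained, as is the instruction in 8b to stop MIFE when an AUD subject on the CRU is thought to be developing hypoadrenalism. The change does not remove every judgement: nausea that could be withdrawal or a drug effect must still be attributed. The amendment makes clear that attribution decides the outcome.
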